7.2 MERS Vaccine Development and Preclinical Studies Using the MVA-MERS-S Vaccine Vector

The experimental vaccine MVA-MERS-S has been studied in several animal models as outlined in the investigator's brochure (IB) (13). More specific primary pharmacology data were obtained in the following models and studies:

- Mouse immunogenicity (Song F et al., 2013)
- Protection from MERS-CoV challenge in transiently transduced hDPPiV mice (Volz A et al., 2015)

- Rat immunogenicity (as part of GLP compliant pivotal nonclinical toxicology study)
- Dromedary camels (Haagmans BL et al., 2016)

To date there is no appropriate non-human-primate model established for MERS, that models human disease in a satisfactory manner.

Table 4 of the investigator brochure summarizes the findings in these models that collectively describe MVA-MERS-S as a vaccine candidate with good immunogenicity, affording protection from virus challenge in two relevant animal models (mice and camels) without significant toxicity.

7.3 Clinical Experience available for MVA-MERS-S

To date, there has been no prior clinical trial experience with the MVA-MERS-S vaccine. This trial will be a first-in-human study for the investigational product MVA-MERS-S.

However, ample clinical experience with the licensed MVA vaccine (Imvanex/Imvamune, Bavaria Nordic, EMA licensing 2013) for protection against smallpox and multiple MVA-vaccine constructs for other infectious diseases (HIV, Influenza, Malaria, Tb, cancer, hepatitis C&B) is available and more than 6,500 patients and healthy volunteers were enrolled in the clinical trials listed in table 15 [13]. The MVA vector has been used extensively in diverse study populations including children, cancer patients and HIV and other immunocompromised individuals. No vaccine-related serious adverse event (SAE) has been reported therein and reported adverse events (AE) were all mild-to-moderate in nature and clearly dose-dependent.

All AEs reported were transient and resolved spontaneously.

7.4 Risk-benefit considerations

The participation in a phase I/ FIM study may not be of a therapeutic benefit to healthy subjects. Known risks related to the pharmacological properties of the investigational compound and/or study modalities are possible. To our best knowledge and judgement, the IMP seems to be safe and no severe side effects and no unacceptable adverse drug reactions (ADR) are expected with this study, as the used MVA vaccine vector has been extensively used in clinical trials for other infectious diseases threats encompassing in >6500 individuals, including children, cancer patients and immunocompromised hosts. The vaccine vector has had an excellent safety profile and unexpected adverse reactions conferred by the antigenic insert are not anticipated.

Preclinical data suggest a favorable safety and tolerability profile. All relevant preclinical studies have been conducted that are needed to start clinical development. Based on available information and the design of the study, the sponsor and the Investigator consider the trial to be ethically acceptable. The duration of confinement, the medical surveillance and the chosen time interval for the sequential dosing of each dosing cohort are considered adequate to ensure safety of the subjects. Special consideration was given to adequate spacing of dosing and frequent safety assessments as mandated and recommended by the regulatory authorities.

During protocol development, processes and data have been identified which are critical to ensure human subject protection and the reliability of trial results.

7.4.1 Potential Risks for Study Participants

7.4.1.1 Phlebotomy

The total amount of blood sampled from a subject will be max. 610 mL (575 mL for the safety and immunogenicity sampling, 35 mL for screening) over 7 months and additional 300 mL for the subjects receiving a 3rd immunization. No more than 500 mL will be drawn in 3 months. These drawn blood volumes should not compromise these otherwise healthy subjects, and are equivalent volumes to voluntary blood donations. There may be minor bruising, local tenderness, presyncopal symptoms associated with venipuncture, or [phlebitis](#) which may subsequently result in thrombosis. These events which will not be documented as AEs if they occur.

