Statistical methods:	
Metric data will be summarized using descriptive statistics (number, mean, standard deviation, minimum, median and maximum). Categorical data will be summarized by using frequency tables (frequency and percent). It is not planned to test any hypotheses in a confirmatory sense.

STUDY SCHEDULES

Table 1a

Phase of study	SCR	Confinement			Ambulatory Visits			Confinement			Ambulatory Visits				End of study
Study day	-28- -2	-1	0	1	3	7	14 (±2)	27	28	29	35	42 (±2)	56 (±3)	84 (±3)	180 (±7)
Informed Consent	√														
I/E Criteria	√	√						√							
Medical History/ De-mographics	√														
Update Medical History		√						√							
Physical Examination	√	√ ^a						√ ^a				√ ^a			√
Height and Weight	√														√ ^c
Vital Signs	√	√	√ ^d	√	√	√	√	√	√ ^d	√	√	√	√	√	√
12-lead ECG	√					√	√		√		√	√			
Ambulatory Visit	√				√	√	√				√	√	√	√	√
Confinement		√	√	√ ^e				√	√	√ ^e					
Dosing			√ ⁱ						√ ⁱ						
Injection site & systemic events/ reactions assessment			√ ^d	√	√	√	√		√ ^d	√	√	√			√
Temperature	√		√ ^d	√	√	√	√		√ ^d	√	√	√	√	√	√
Alcohol Breath Test	√	√						√							
Discharge				√						√					
Training/ Dispensing subject diary			√						√						
Review/ Collection of subject diary				√	√	√	√	√		√	√	√	√	√	√
Adverse Events & Concomitant medication			√ ^d	√	√	√	√	√	√ ^d	√	√	√	√	√	√
Laboratory Analysis															
Phase of study	SCR	Confinement			Ambulatory Visits			Confinement			Ambulatory Visits				End of Study
Study day	-28- -2	-1	0	1	3	7	14 (±2)	27	28	29	35	42 (±2)	56 (±3)	84 (±3)	180 (±7)
Troponin T	√					√	√		√		√	√			√
Safety Lab blood (Clinical Chemistry, Hematology)	√	√		√	√	√	√	√		√	√	√			√
Safety Lab Urine	√	√				√	√	√			√	√			√
HIV/HBV/HCV Serology	√														
Urine Drug Screen	√	√						√							
Pregnancy Test	√ ^h	√ ^g						√ ^g							√ ^h
Anti-MVA-MERS Elisa			√			√	√		√		√	√	√	√	√
Neutralization Assay			√			√	√		√		√	√	√	√	√
T-cell response			√			√	√		√ ^f		√	√	√	√	√
RNA blood sample storage			√	√	√	√			√ ^f	√	√				

Innate immunity			√	√	√	√			√	√	√				
PBMC freezing and plasma aliquots			√	√	√	√	√		√ _f	√	√	√	√	√	√

Table 2b**3rd boost vaccination 8-16 months after initial vaccination**

Phase of study	Phone Call	Dosing	Ambulatory Visits				End of study
Study day	≥ - 7	0	1	3	7	14 (±2)	28(±2)
Informed Consent		√ _f					
I/E Criteria		√ _f					
Update Medical History		√ _f					
Physical Examination		√ _{af}					
Weight		√ _{fc}					
Vital Signs		√ _d	√	√	√	√	√
12-lead ECG		√ _f					

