9.4.10.3.4 Ambulatory Visits

Subjects will return to the study ward for ambulatory visits on study day 3, 7 and 14 (± 2), after the first vaccination and on study day 35, 42 (± 2), 56 (± 3), 84 (± 3) after the second vaccination. On the ambulatory visits the following events will be performed:

- Targeted Physical Examination (only on day 42)
- Vital signs/ Temperature
- 12-lead ECG (only on day 7, 14, 35, 42)
- Injection Site reaction & systemic events/ reaction assessment (only on day 3, 7, 14, 35 and 42)
- Safety Laboratory (Urine) (only on day 7, 14, 35, 42)
- Safety Laboratory (Blood) (only on day 3, 7, 14, 35, 42)
- Blood sampling for troponin (only on day 7, 14, 35, 42)
- Blood sampling for humoral immunogenicity (only on day 7, 14, 35, 42, 56, 84)
- Blood sampling for cellular response (only on day 14, 42, 56, 84)
- PBMC freezing and plasma aliquots
- Blood sampling for RNA storage (only on day 3, 7, 35)
- Blood sampling for innate immunity (only on day 3, 7, 35)
- Adverse events assessment
- Concomitant medication assessment
- Collection and review of diary

9.4.10.3.5 Ambulatory vaccination and subsequent ambulatory visits (only for subjects who gave consent to the study extension)

Subjects will return to the study ward for an ambulatory vaccination visit 12 months (± 4 months) after the first immunization.

The following interventions will be performed:

- Informed Consent
- I/E Criteria check
- Update medical history
- Weight
- Physical examination
- Vital signs / Temperature
- 12-lead ECG
- Injection Site reaction & systemic events/reaction assessment
- AE/ConMed
- Alcohol Breath Test
- Urine Drug Screen
- Urine Pregnancy Test
- Safety Laboratory (Urine/Blood)
- Blood sampling for humoral immunogenicity
- Blood sampling for cellular response
- PBMC freezing and plasma aliquots
- Blood sampling for RNA storage
- Blood sampling for troponin
- Blood sampling for innate immunity
- Dosing
- Training on subject diary

After dosing the following events will be performed **at 2 h, 4 h and 6 h**:

- Vital signs (and at 0 h, before dose administration)
- Temperature (and at 0 h, before dose administration)
- (AE)/ConMed (and at 0 h, before dose administration)
- Injection site reactions & systemic events/reactions assessment

Subjects will return to the study ward for ambulatory visits on study day 1, 3, 7 and 14 (± 2), after the third vaccination.

On the ambulatory visits the following events will be performed:

- Vital signs/ Temperature

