9.5.2.8.1 Bio-Chemistry

Blood samples (4.9 mL) for serum biochemistry will be collected into a lithium heparin separator tube at the time points described in Table 1. The following parameters will be assessed:

Sodium	Aspartate transaminase (AST)
Potassium	Alanine transaminase (ALT)
Calcium	Alkaline phosphatase (ALP)
Urea	Gamma glutamyl transferase (GGT)
Creatine kinase (total)	Total bilirubin
Albumin	Glucose
Total protein	Pancreas specific amylase
Creatinine	Lactate dehydrogenase (LDH)
Creatinine clearance (MDRD) (only at Screening)	C reactive protein (CRP)

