9.5.2.8.2 Hematology

A 2.7 mL sample of blood will be drawn into a tube containing potassium ethylene diamine tetra-acetic acid (**EDTA**) anticoagulant at the time points described in Table 1. The following parameters will be assessed:

Hemoglobin	Mean corpuscular hemoglobin concentration (MCHC)
Hematocrit	White blood cell (WBC) count; total and differential
Red blood cells (RBC)	Neutrophils
Mean corpuscular volume (MCV)	Lymphocytes

	Monocytes
Platelet count	Eosinophils
Mean corpuscular hemoglobin (MCH)	Basophils
Reticulocytes	

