9.5.3.1.3 T cell IFN- γ ELISPOT

The magnitude, kinetics and epitope targets of MVA-MERS T-cell responses will be assessed by IFN- γ ELISpot assay. The assay will be performed on cryopreserved PBMC samples (from 4 x 9 mL EDTA tubes) obtained at the time points described in Table 1. The analysis will be performed in the Virus-Immunology Research Laboratory, Heinrich-Pette-Institute, Hamburg, Germany according to the process defined in the Laboratory Manual.

Blood samples (36 mL) for T cell immunogenicity analysis (2 x 9 mL for ELISpot and 2 x 9 mL for ICS) will be drawn by direct venipuncture into four EDTA tubes, capped and mixed by inversion (x3). The actual time that the sample was obtained will be recorded on the source documents. After applying a tourniquet, venous blood will be taken with a disposable needle.

The labels will contain the following information:

Study Number

Study Day and Time point

Subject Identifier

9.5.3.1.4 Sample preservation for Intracellular Cytokine Staining for MERS-S-specific CD4 and CD8 T cell responses

The magnitude and kinetics of MERS-S-specific CD4 and CD8 T-cell responses will be determined from cryopreserved PBMC at the time points described in Table 1 using flow cytometry (from 2 x 9 mL EDTA tubes as above). The analysis will be performed by [name] and [name] [name]'s group at the UKE, hosted in the Virus-Immunology Research Laboratory, Heinrich-Pette-Institute, Hamburg, Germany according to the process defined in the Laboratory Manual.

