9.5.3.1.6 Innate immunity

To evaluate early innate immunity gene expression signatures cryopreserved PBMC at the time points described in Table 1 will be analyzed using flow cytometry (from 2 x 9 mL EDTA tubes). Furthermore, plasma obtained after centrifugation of the EDTA tube will be analyzed via luminex multiplex assays.

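### Section 7.4.1.1 contradicts itself: its 575 mL post-screening maximum implies about 519 mL in 85 days, against its own limit of 500 mL in 3 months

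*Protocol*

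**What the plan says.** Section 7.4.1.1 (Phlebotomy) gives the maximum as "max. 610 mL (575 mL for the safety and immunogenicity sampling, 35 mL for screening) over 7 months", with a further 300 mL for subjects who take the third vaccination. It then sets a limit: "No more than 500 mL will be drawn in 3 months".

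Tube volumes are given assay by assay in sections 9.5.2.8 and 9.5.3.1. The largest is the cellular sample: "Blood samples (36 mL) for T cell immunogenicity analysis (2 x 9 mL for ELISpot and 2 x 9 mL for ICS". Innate immunity is measured "from 2 x 9 mL EDTA tubes". The protocol does not say whether these are additional tubes or part of the T-cell tubes on days when both are due. Section 9.5.3.1 says that the immunogenicity volumes are maximum amounts and leaves exact volumes to the laboratory manual.

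The sampling days appear in two places. The row "T-cell response" of Table 1a is marked on days 0, 7, 14, 28, 35, 42, 56, 84 and 180. Section 9.4.10.3.4 lists, for the ambulatory visits, "Blood sampling for cellular response (only on day 14, 42, 56, 84", which leaves out days 7 and 35.

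**The concern.** Sampling is concentrated around the two vaccinations. After day 84 only one scheduled draw remains, on day 180. A 7-month maximum of 575 mL can respect a 500 mL limit in 3 months only if at least 575 - 500 = 75 mL is reserved for day 180, and the stated tubes for that visit come to less.

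The limit is a subject-protection statement, and the risk section's reassurance about blood loss rests on it. A site cannot tell from the protocol whether following the schedule keeps a subject within the limit. The disagreement on T-cell days is a second, separate inconsistency. It leaves the site without a clear instruction for two 36 mL draws.

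**Working it through.** **Inputs** (volume per draw, and draws counted from Table 1a unless noted)

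| Sample | mL | Section | Draws, day -1 to 84 | Day 180 |
|---|---|---|---|---|
| Biochemistry + hematology | 4.9 + 2.7 = 7.6 | 9.5.2.8.1, 9.5.2.8.2 | 9 (days -1, 1, 3, 7, 14, 27, 29, 35, 42) | 1 |
| Troponin T | 4.9 | 9.5.2.8.6 | 5 (days 7, 14, 28, 35, 42) | 1 |
| Serum pregnancy test (women) | 7.5 | 9.5.2.8.5 | 2 (days -1, 27) | 0 |
| ELISA, same serum for neutralization | 7.5 | 9.5.3.1.1, 9.5.3.1.2 | 8 (days 0, 7, 14, 28, 35, 42, 56, 84) | 1 |
| T cell | 36 | 9.5.3.1.3 | 8 by Table 1a; 6 by the visit text (no day 7, 35) | 1 |
| RNA | 2.5 | 9.5.3.1.5 | 7 (days 0, 1, 3, 7, 28, 29, 35) | 0 |
| Innate immunity | 2 x 9 = 18 | 9.5.3.1.6 | 7 (same days as RNA) | 0 |

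PBMC storage has no volume of its own and is assumed to use the same tubes.

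**Step 1. Day-180 draw.** 7.6 + 4.9 + 7.5 + 36 = 56.0 mL.

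**Step 2. Tube sums, day -1 to 84, screening excluded.** The part common to all readings is 9 x 7.6 + 5 x 4.9 + 8 x 7.5 + 7 x 2.5 = 68.4 + 24.5 + 60 + 17.5 = 170.4 mL for men. Women add 2 x 7.5 = 15, giving 185.4 mL. The T-cell and innate tubes are then added (women shown in full; men are 15 mL lower):

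- Visit text, separate tubes: 185.4 + 6 x 36 + 7 x 18 = 527.4 (men 512.4).
- Visit text, shared on days 0 and 28: 185.4 + 216 + 5 x 18 = 491.4 (men 476.4).
- Table 1a, separate tubes: 185.4 + 8 x 36 + 7 x 18 = 599.4 (men 584.4).
- Table 1a, shared on days 0, 7, 28 and 35: 185.4 + 288 + 3 x 18 = 527.4 (men 512.4).

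**Step 3. Reproducing the stated 575 mL.** Adding 56 mL to each:

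- Visit text separate, and Table 1a shared: 583.4 (women) and 568.4 (men), i.e. +1.5% and -1.1% against 575. Both readings reproduce the figure.
- Table 1a separate: 655.4 and 640.4 (+14% and +11%). Does not reproduce it.
- Visit text shared: 547.4 and 532.4 (-4.8% and -7.4%). Does not reproduce it.

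**Step 4. The limit, from the stated total alone.** 575 - 56 = 519 mL between day -1 and day 84. The excess is 519 - 500 = 19 mL, or 19/500 = 3.8%. Equivalently, a 500 mL limit would cap the post-screening maximum at 500 + 56 = 556 mL. This step does not depend on tube sharing or on which T-cell schedule applies.

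**Step 5. Screening blood.** The stated screening tubes sum to 7.6 + 4.9 + 2 x 7.5 = 27.5 mL, against 35 mL in section 7.4.1.1. Screening runs from day -28 to day -2. If it falls in roughly the last week before dosing, it shares 3 months with day 84. For example, day -2 to day 84 is 86 days, and the stated figures then give 519 + 35 = 554 mL.

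**Step 6. The T-cell days.** Days 7 and 35 are worth 2 x 36 = 72 mL of T-cell blood per subject. If tubes are shared, the net difference between the two schedules is 527.4 - 491.4 = 36 mL.

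**The case against.** The strongest defence is that these are ceilings. Section 9.5.3.1 calls the immunogenicity volumes maximum amounts, the 575 mL is itself a maximum, and the laboratory manual that fixes the real volumes is not at hand. One reading, the visit text with shared tubes, stays under the limit at 491/476 mL, and a sum below 575 is compatible with a stated maximum. The excess from the protocol's own total is under 4%.

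Much of this stands. It rules out any claim that subjects will be over-drawn. It does not remove the contradiction, because a stated maximum is set against a stated limit in one paragraph, so comparing maxima is the right test. A smaller real draw on day 180 would leave more of the 575 mL in the first 85 days. The reading that stays below 500 mL depends on sharing that the protocol does not state, and both readings that reproduce 575 mL exceed the limit.

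A reader might infer four stronger points that the documents do not support:

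- **That the table/text mismatch causes the excess.** The 519 mL does not depend on it, and the visit text with separate tubes already gives 527/512 mL. Only under sharing does the choice of schedule move the tube sum across 500 mL.
- **That the limit is broken on every reading.** This needs screening close to dosing. With screening on day -28, the full span to day 84 is 112 days. A 3-month window from day -28 ends near day 63 and drops the day-84 draw (7.5 + 36 = 43.5 mL). For women on the visit text with shared tubes that gives 491.4 + 27.5 - 43.5 = 475.4 mL.
- **That the early cellular response is lost if days 7 and 35 are omitted.** PBMC are frozen on those days under both Table 1a and section 9.4.10.3.4, and the ELISpot and cytokine assays use cryopreserved cells. These objectives are exploratory (section 8.5).
- **That the 300 mL boost figure is wrong.** The tubes give 6 x 7.6 + 2 x 4.9 + 4 x 7.5 + 4 x 36 + 4 x 2.5 + 4 x 18 = 311.4 mL separate, or 275.4 mL if shared on days 0 and 7. That range brackets 300.

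**Conclusion.** The point holds as an internal contradiction in section 7.4.1.1. The post-screening maximum implies about 519 mL in 85 days against a limit of 500 mL in 3 months, before any screening blood in the same period. The reason is that only 56 mL of the total falls outside that window.

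The 519 mL rests on the stated tube volumes for day 180 and on the Table 1a visit days. The tube sums of 476 to 599 mL also assume that PBMC storage draws no extra blood. The top of that range is the reading furthest from the stated 575 mL and should not be taken as the expected volume.

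The disagreement between Table 1a and section 9.4.10.3.4 on days 7 and 35 is real and separate. It can enlarge the excess but is not its source. No primary or secondary endpoint is affected. This is a consistency correction to a safety statement and should be made.

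**What to change.** Reconcile section 7.4.1.1, Table 1a and section 9.4.10.3.4. Specifically:

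- State one set of T-cell sampling days and use it in both the table and the visit text.
- State whether innate-immunity and T-cell samples share tubes on days when both are due.
- Recompute the 3-month maximum and the overall maximum from the final schedule, with screening included and with men and women shown separately or the larger figure used. Explain the 35 mL for screening against the 27.5 mL of listed tubes.
- Make the limit, the total and the schedule agree, whether by restating a figure or by changing the sampling. The volumes are for the sponsor to set.

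The cost is amendment wording and a short recalculation, possibly with fewer exploratory tubes. If the subject information repeats these volumes, it needs the same correction, for which section 9.9 already provides.

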8.2 Primary Endpoints

The safety, tolerability, and reactogenicity of the experimental vaccine MVA-MERS-S will be measured as followed:

- Occurrence of solicited local reactogenicity signs and symptoms for 14 days following the vaccination (see Table 3)
- Occurrence of solicited systemic reactogenicity signs and symptoms for 14 days following the vaccination (see Table 4 and Table 5)
- Occurrence of unsolicited AEs for 28 days following the vaccination
- Change from baseline of safety laboratory measures
- Occurrence of SAEs throughout the study period

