9.5.2.8.9 Reactogenicity

To assess reactogenicity after each immunization body temperature and reaction are recorded for at least 14 days after vaccination or until any symptoms resolved if longer. According to the defined time frame of ± 2 days for the ambulatory visit on day 42 recording might be shortened to day 40. During confinement at the study ward temperature and solicited injection site and systemic reactions will be assessed and recorded by a designated member of the study team. After dismissal subjects are asked to maintain a diary to record daily temperature and solicited (expected) injection site and systemic reactions for 14 days after each dosing. Subjects will be asked to maintain a second diary for another 14 days to record medicinal events. As described above, the second diary after the second immunization should be maintained at least until day 40. Subjects will be trained on the thermometer and diary use.

The following items will be recorded:

- Daily temperature (incl. the method by which it was taken)
- Daily measurement of intensity grade of all other solicited (expected) injection site and systemic reactions
- Action taken for each recorded event (none, medication taken, physician consulted, hospitalization)

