9.7 Adverse Events

9.7.1 Definition of Adverse Events, Period of Observation, Recording of Adverse Events

An **Adverse Event (AE)** is any untoward medical occurrence in a clinical investigation subject administered an Investigational Medicinal Product (IMP) and that does not necessarily have a causal relationship with this treatment. An AE can therefore be any unfavorable and unintended sign (including an abnormal laboratory finding), symptom, disease or exacerbation of a pre-existing condition temporally associated with the use of a medicinal (test) product, whether or not considered related to the medicinal product (ICH Guidance E2A 1995).

All AEs, including those associated with the protocol, are collected from the time after first administration of IMP until the defined follow-up period and are to be recorded on the appropriate AE pages in the eCRF and in source documents. Where possible, a diagnosis rather than a list of symptoms should be recorded. If a diagnosis has not been made then each symptom should be listed individually.

A solicited AE is a predetermined event occurring within 14 days after application of IMP, which may reflect safety concerns related to the investigational product. The solicited AEs for this study include:

- Swelling, redness/ erythema, induration, hematoma or pain at site of injection
- Fever
- Chills
- Myalgia (described to the subject as generalized muscle aches)
- Arthralgia (described to the subject as generalized joint aches)
- Fatigue
- Headache
- Gastrointestinal symptoms (nausea, vomiting, abdominal pain, loose stool and/or diarrhea)
- Malaise

All AEs must be followed to closure (the subject's health has returned to his/her baseline status or all variables have returned to normal), an outcome is reached, stabilization (the investigator does not expect any further improvement or worsening of the event), or the event is otherwise explained regardless of whether the subject is still participating in the study. When appropriate, medical tests and examinations are performed so that resolution of event(s) can be documented.

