9.7.2 Severity Categorization of AEs

The severity of AEs must be recorded during the course of the event including the start and stop dates for each change in severity. An event that changes in severity should be captured as a new event. Worsening of pre-treatment events, after initiation of investigational medicinal product, must be recorded as new AEs.

The medical assessment of severity is determined by using the following definitions:

- Mild:** A type of AE that is usually transient and may require only minimal treatment or therapeutic intervention. The event does not generally interfere with usual activities of daily living.
- Moderate:** A type of AE that is usually alleviated with additional specific therapeutic intervention. The event interferes with usual activities of daily living, causing discomfort but poses no significant or permanent risk of harm to the research subject.
- Severe:** A type of AE that interrupts usual activities of daily living, or significantly affects clinical status, or may require intensive therapeutic intervention.

Additionally, the severity of AEs will be graded according to the toxicity scale described in section 9.7.11. If the AE is not defined in the tables of section 9.7.11 the severity will be graded according to NCI CTCAE (current version).

The severity assessment is described more detailed in section 9.7.11.

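### Two adverse event recording rules contradict the primary safety endpoint: the venepuncture exclusion in 7.4.1.1 and the day-40 diary stop after dose 2 in 9.5.2.8.9

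*Protocol*

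**What the plan says.** **Venepuncture events.** Section 7.4.1.1 warns: "There may be minor bruising, local tenderness, presyncopal symptoms associated with venipuncture". It adds phlebitis, which may lead to thrombosis, and closes with "These events which will not be documented as AEs if they occur". Section 9.7.1 gives the general rule: "All AEs, including those associated with the protocol, are collected from the time after first administration of IMP". Section 9.7.7 says AEs and SAEs go into the eCRF whether or not they are attributed to the study intervention. Section 9.7.3 has the investigator classify each AE as related or not related, and the second category covers events readily explained by other factors.

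**Diaries.** Section 8.2 defines the solicited primary endpoints over 14 days after vaccination, and the unsolicited one as "Occurrence of unsolicited AEs for 28 days following the vaccination". Section 9.5.2.8.9 asks for at least 14 days of reactogenicity recording, longer if symptoms persist. It then allows recording after dose 2 to end at day 40, because the day-42 visit has a window of ±2 days. A second diary is to run for a further 14 days, yet the section adds that "the second diary after the second immunization should be maintained at least until day 40".

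**The concern.** Safety is the primary objective of this first-in-human trial, and the primary endpoints are occurrences of solicited events, unsolicited AEs and SAEs. Both rules act at the point of collection. The SAP is not shown, but no SAP can recover an event that was never written down.

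The venepuncture sentence applies a causality filter before recording. The rest of the protocol works in the opposite order: record first, then attribute under 9.7.3. Because the exclusion has no severity or seriousness limit, a thrombosis following phlebitis that met a criterion in 9.7.7.2 would be left undocumented by 7.4.1.1 and required by 9.7.7. SAE occurrence is itself a primary endpoint.

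The day-40 sentences let the observation window after dose 2 fall short of the endpoint definition. Section 9.5.3.5.1 tabulates AEs by dosage level and injection. No shortening is stated for dose 1, although its day-14 visit has the same ±2 window, so the injections being compared may not have been observed for equal times.

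**Working it through.** **Sample size.** There is no formula to reproduce. Section 9.8.2 sets N = 24 (12 per dose level) by precedent, and 9.8.1.3 plans no confirmatory test.

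**1. The recording rules side by side**

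| Section | Venepuncture-associated event after the first dose |
|---|---|
| 7.4.1.1 | not documented as an AE; no severity or seriousness limit |
| 9.7.1 | collected, as a protocol-associated AE |
| 9.7.7 | recorded whatever the attribution, including when serious |

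The first row cannot be followed together with the other two.

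**2. Is attribution ambiguous in practice?** Table 1a schedules immunogenicity blood on days 0 and 28, the two dosing days, and safety blood on days 1 and 29. The schedule for the third vaccination likewise has draws on its days 0 and 1. Presyncopal symptoms are not on the solicited list in 9.7.1 and have no anatomical site that would separate needle from vaccine. On those days the same symptom is either an unsolicited AE or absent from the database, depending on a judgement that need not be documented.

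**3. What one unrecorded subject is worth.** Exact (Clopper-Pearson) 95% upper limits with n = 12:

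- 0/12: upper = 1 − 0.025^(1/12) = 0.2646, or 26.5%.
- 1/12: upper is the p solving (1 − p)^12 + 12p(1 − p)^11 = 0.025, giving 0.3848, or 38.5%.

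The point estimate moves from 0% to 1/12 = 8.3%.

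The protocol gives no event rates, so the following rates are assumptions. The chance of at least one affected subject in 12 is 1 − (1 − p)^12: 46% at p = 5%, 72% at 10% and 93% at 20%. At the lower rates a cohort may well contain only one case or none, so losing one changes the reported result.

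**4. Diary arithmetic after dose 2 (day 28)**

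- Solicited window in 8.2: 28 + 14 = day 42.
- Permitted stop: day 40, and 40 − 28 = 12 days. Up to 14 − 12 = 2 days are lost, and 2/14 = 14%.
- Second diary, a further 14 days: about days 43 to 56, ending with the unsolicited window at 28 + 28 = day 56.
- Stated minimum for that diary: day 40, before its first day.

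**The case against.** **On venepuncture.** The exclusion is narrower than a quick reading suggests. It concerns blood sampling, the presyncopal symptoms are those tied to venepuncture, and thrombosis appears only as a sequel of phlebitis. Injection-site reactions are solicited and checked at fixed times, and an investigator attends for at least 30 minutes after vaccination. This stands as a limit on how many events could be lost. It does not resolve the contradiction with 9.7.1 and 9.7.7, nor does it supply the missing severity limit.

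A reader might also infer a conflict with 9.5.2.8.10, where phlebitis is Grade 3. That does not hold: the scale grades reactions resulting from the IMP, which is a different cause.

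**On the diaries.** The shortening is openly stated and only permitted, and unresolved symptoms are still followed. The exposure is therefore mainly to new onsets on days 13 and 14 after dose 2. Two of 14 days is a share of calendar time, not of expected reactions. All of this stands.

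Read literally, the second-diary sentence would leave days 41 to 56, 16 of 28 (57%), without a required diary. That figure should not be used as a loss of endpoint data. The sentence is probably a drafting error and states a minimum. Table 1a keeps diary review at day 56 and later, and AEs are elicited by questioning at days 42, 56, 84 and 180.

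**On severity changes.** Section 9.7.2 says "An event that changes in severity should be captured as a new event", and a reader might infer that this inflates the endpoint. An assumed Grade 1-2-1 course would give three event records, but the subject count and maximum grade are unchanged. The endpoints in 8.2 are occurrences, 9.5.3.5.1 also tabulates subjects, and the holding rules in 9.3.3.3 count injections or individuals. How to collapse segments is ordinary SAP content, so this is not part of the point.

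**Conclusion.** The point holds for two collection rules. Section 7.4.1.1 contradicts 9.7.1 and 9.7.7. Section 9.5.2.8.9 falls short of the windows in 8.2 and contradicts its own 14-day requirement and second-diary period. Both should be corrected, though neither puts the endpoint as a whole at risk.

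Size: for venepuncture, one unrecorded subject in a cohort of 12 separates an upper limit of 26.5% from one of 38.5%. How often that would happen cannot be estimated, because the protocol gives no rate. For the diaries, up to 2 of 14 solicited days after dose 2, plus an unclear instruction for the later diary. What is lost there is late prompted capture, since later visits still ask about AEs.

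A reader might conclude that the primary safety endpoint is distorted overall. The documents do not support that: no net bias is shown, and the safeguards above remain in place. The conclusion assumes that sites would apply 7.4.1.1 as written and that the second diary follows directly on the first.

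**What to change.** 1. Delete the last sentence of 7.4.1.1. Record these events like any other AE, with venepuncture entered as the alternative cause in the 9.7.3 assessment. At minimum, limit the exclusion to minor, non-serious events and state the exception in 9.7.1 and 9.7.7.
2. In 9.5.2.8.9, run the first diary to 14 days and the second to 28 days after each dose, whatever the visit date. Collect each at the next scheduled visit. Correct both day-40 sentences so that they match 8.2.

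Cost: amendment wording, a revised diary instruction, and a few more trivial AEs to record. No extra visits or samples are needed.
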